Page 40 - Randomization Code	The randomization will be performed with stratification to study sites smoking habits and Baseline PD measurement in balanced blocks, each block containing 6 subjects. A total number of 48 blocks will be prepared for a total of 288. Each site will receive 4 types of lists by the defined stratification (smokers with PD 5 mm, smokers with PD 6-8 mm, non-smokers with PD 5 mm and non-smokers with PD 6-8 mm). This number already includes 10 blocks for spare.	The randomization will be performed with stratification to study sites smoking habits and Baseline PD measurement in balanced blocks, each block containing 6 subjects (3 per treatment Subgingival debridement + PerioChip® and 3 per treatment Subgingival debridement alone). A total number of 56 blocks will be prepared for a total of 336 subjects. Randomization blocks will be sent to the sites by the study data management Statistician . Each site will receive 4 types of lists by the defined stratification (smokers with PD 5 mm, smokers with PD 6-8 mm, non-smokers with PD 5 mm and non-smokers with PD 6-8 mm). Additional blocks will be provided to the sites according to the recruitment rate . This number already includes 10 blocks for spare.
Page 41 – Sample size	Statistical significance level was set to 4% since an Interim Analysis, that will use 1% of the total significance level, is planned.	Statistical significance level for all statistical analysis was set to 4% since an Interim Analysis that will use 1% of the total significance level, is planned 5.
Page 42 - Analysis population	Intent-to-treat (ITT) population – all patients randomized for one of the treatment arms and treated with at least one chip of study treatment or underwent Subgingival debridement will be used for all safety evaluations	Intent-to-treat (ITT) population – all patients randomized for one of the treatment arms and treated with at least one chip of study treatment or underwent Subgingival debridement will be used for assessments related to efficacy and all safety evaluations

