148-151	A total of 246 patients in at least five clinical sites will be randomized. 123 patients for the Subgingival debridement + PerioChip® arm, and 123 patients for Subgingival debridement alone arm	A total of 290 patients in at least nine clinical sites will be randomized. At least 123 patients for the Subgingival debridement + PerioChip® arm, and at least 123 patients for Subgingival debridement alone arm will complete all required study visits, considering withdrawal rate estimation of between 12%-15%
Protocol Synopsis - Inclusion Criteria #5		
177-183	The patient has at least one implant in the oral cavity with clinical and radiographical signs of peri-implantitis. In the affected implant, at least one of the four aspect measured (mesio-buccal, mid-buccal, disto-buccal and mid-lingual) must show radiographic evidence of bone loss of at least 3 mm from implant shoulder, and at least 2 mm distal and mesial supporting bone left from the apex to the coronal direction, in combination with bleeding and/or suppuration on probing and a peri-implant Probing Depth (PD) of 5-8 mm.	The patient has at least one implant in the oral cavity with clinical and radiographical signs of peri-implantitis. In the affected implant, at least one of the four aspects measured [mesio-buccal (MB), mid-buccal (MiB), disto-buccal (DB) and mid-lingual (MiL)] must show radiographic evidence of bone loss of at least 3 mm from implant shoulder, and at least 2 mm distal and mesial supporting bone left from the apex to the coronal direction, in combination with bleeding and/or suppuration on probing and a peri-implant Probing Depth (PD) of 5-8 mm.

Dexcel Pharma Technologies Ltd

Protocol Synopsis - Exclusion Criteria #10		
204-207	Patients chronically (i.e. two weeks or more) treated with non-steroidal anti-inflammatory drugs (NSAIDs) or any medications known to affect soft tissue condition (excluding treatment of Acetylsalicylic acid \leq 100 mg/day).	Patients chronically (i.e. two weeks or more) treated with non-steroidal anti-inflammatory drugs (NSAIDs) or any medications known to affect soft tissue condition (excluding treatment of Acetylsalicylic acid \leq 100 mg/day). A comprehensive list can be found in the Patient information sheet – list of prohibited medications.
Protocol Synopsis - Exclusion Criteria #11 (New)		

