2. STATISTICAL METHODS

2.1 General

The change in efficacy parameters, PD, R and RAL during the 24 week treatment, will be modelled using a linear-mixed model (SAS® 9.3 Mixed Procedure) with treatment as fixed factors. Patient and pocket will be entered as random effects. The treatment-by-center interaction will be tested and if achieve statistical significance of $\leq 5\%$ will be added to the model as covariate. The analysis will be adjusted to the following covariates known to have influence on the efficacy parameters: age, gender, smoking status and baseline measurements. The adequacy of the Mixed Model will be checked and if needed a normalizing transformation will be performed. This model will be used for the reduction in PD, R and for improvement in RAL.

Contrasts with 95% Confidence Interval (C.I.) for the difference or ratio between the changes will be computed.

The Paired T-test or Signed rank test for two means (paired observations) (as is appropriate) will be applied for testing the statistical significance of the decrease in PD at each time point within each study group.

The two-sample T-test or Non-parametric Wilcoxon-Mann-Whitney Rank sum test for independent samples (as is appropriate) will be applied for testing the statistical significance of the difference in the percent PD decrease from baseline between the study groups.

Patients may have multiple pockets being treated. All treated pockets will be taken into account to create a by-pocket analysis in addition to the by-patient analysis.

Corresponding 95% C.I. for the difference between treatments not including zero for linear model, or 95% C.I. for the ratios between treatments not including unity for the log-linear regression will prove superior to treatment with PerioChip® versus Subgingival debridement.

Analysis for the number of pockets with at least 1 mm and at least 2 mm reduction in PD, and analysis for BOP for the target implant/s measured at each visit will be analyzed by a Chi-square test or Fisher's exact test as is appropriate.

Logistic regression will be applied for testing the above differences with adjustment to smoking status, Gingival Index (GI), medical center and other suspected confounders, if found. Odds Ratio and 95% Confidence Interval will be calculated using the Logistic model.

Similar mixed models for PD, R and RAL with time as a fixed repeated covariate will be used to reveal the changes of these parameters over time.

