3.3.1 Principal Analysis

The change in efficacy parameters, PD, during the 24 week treatment, will be modelled using a linear-mixed model (SAS® 9.3 Mixed Procedure) with treatment as fixed factors. Patient and pocket will be entered as random effects. Interactions between treatment and the covariates will be tested and if achieve statistical significance of $\leq 5\%$ will be added to the model as covariate. The analysis will be adjusted to the following covariates known to have influence on the efficacy parameters: age, gender, smoking status, site and baseline measurements. The adequacy of the Mixed Model will be checked and if needed a normalizing transformation will be performed.

Contrasts with 95% C.I. for the difference between the changes by week will be computed.

The Paired T-test or Signed rank test for two means (paired observations) (as is appropriate) will be applied for testing the statistical significance of the decrease in PD at each time point within each study group.

The two-sample T-test or Non-parametric Median test for independent samples (as is appropriate) will be applied for testing the statistical significance of the difference in the PD decrease from baseline between the study groups.

Categorical analysis will be applied for PD change at week 24, using median value calculated overall subjects. Logistic regression will be applied for categorical PD change with adjustment to baseline measure, age, gender, site and smoking status. Interactions between treatment and the covariates will be tested and if found statistically significant, will be added to the model.

Analysis of Variance (ANOVA) will be applied for analysing PD change at week 24, with adjustment to baseline measure, age, gender, site and smoking status. Interactions between treatment and the covariates will be tested and if found statistically significant, will be added to the model.

Missing data will be handled for imputation the primary endpoint data using the MMRM model (Mixed-effect Model for Repeated Measures), which is based on MAR (missing at random) assumption.

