3.5 Exploratory Analysis

- PD, BOP and RAL measurements at week 24 compare to baseline in Responders patients. Responders patients are those patients which demonstrated at week 24 PD reduction of at least 1 mm from baseline PD of 5 mm or PD reduction of at least 2 mm from baseline PD of 6-8 mm inclusive.
- PD and BOP measurements at weeks 8 and 12 compared to baseline.
- Recession (R) and Relative Attachment Levels (RAL) measurements at weeks 8, 12, 16 and 24 compare to baseline.
- PD measurement at week 12 and 16 compared to week 24.
- PD, BOP, RAL and R measured at weeks 8, 12, 16 and 24 for all 4 sites (mesio-buccal, mid-buccal, disto-buccal and mid-lingual), surrounding the selected target implant/s, compared to baseline.

The statistical methods described in the subsequent paragraphs will be used for analysis of both primary and secondary endpoints. The change in efficacy parameters, PD, R and RAL during the 24 week treatment, will be modelled using a linear-mixed model (SAS® 9.3 Mixed Procedure) with treatment as fixed factors. Patient and pocket will be entered as random effects. The interactions between treatment and the covariates will be tested and if achieve statistical

significance of $\leq 5\%$ will be added to the model as covariate. The analysis will be adjusted to the following covariates known to have influence on the efficacy parameters: age, gender, smoking status and baseline measurements. The adequacy of the Mixed Model will be checked and if needed a normalizing transformation will be performed. This model will be used for the reduction in PD, R and for improvement in RAL.

Contrasts with 95% C.I. for the difference between the changes by week will be computed.

The Paired T-test or Signed rank test for two means (paired observations) (as is appropriate) will be applied for testing the statistical significance of the decrease in PD at each time point within each study group.

The two-sample T-test or Non-parametric Median test for independent samples (as is appropriate) will be applied for testing the statistical significance of the difference in the PD decrease from baseline between the study groups.

Patients may have multiple pockets being treated. All treated pockets will be taken into account to create a by-pocket analysis in addition to the by-patient analysis.

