Analysis for the number of pockets with at least 1 mm and at least 2 mm reduction in PD, and analysis for BOP for the target implant/s measured at each visit will be analyzed by a Chi-square test or Fisher's exact test as is appropriate.

Logistic regression will be applied for testing the above differences with adjustment to smoking status, GI, medical center and other suspected confounders, if found. Odds Ratio and 95% Confidence Interval will be calculated using the Logistic model.

Similar mixed models for PD, R and RAL with time as a fixed repeated covariate will be used to reveal the changes of these parameters over time.

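### Site is a randomisation stratum but is left out of two of the SAP's three mixed-model covariate lists, and the BOP logistic model names no baseline PD

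*SAP*

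**What the plan says.** **Randomisation.** The version 1 to version 2 entry in the protocol's summary of changes, under Randomization Code, reads: "The randomization will be performed with stratification to study sites smoking habits and Baseline PD measurement in balanced blocks". It adds: "Each site will receive 4 types of lists by the defined stratification". The four lists cross smoking with baseline PD of 5 mm or 6-8 mm, and blocks hold 6 patients. Later entries for section 7.2 remove only the block counts. The version 8 entry for the number of patients in the synopsis states: "A total of 290 patients in at least nine clinical sites will be randomized".

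**Primary endpoint.** SAP 3.3.1, Principal Analysis, fits a mixed model adjusted for "age, gender, smoking status, site and baseline measurements". The logistic model and the ANOVA in the same section also include site.

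**General and exploratory sections.** The mixed models in SAP 2.1 and 3.5 adjust for "age, gender, smoking status and baseline measurements", without site. Section 2.1 brings centre in only as an interaction: "The treatment-by-center interaction will be tested and if achieve statistical significance of" 5% or less, it joins the model. Section 3.5, although headed exploratory, says: "The statistical methods described in the subsequent paragraphs will be used for analysis of both primary and secondary endpoints".

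**Secondary endpoints.** SAP 3.4 lists the four endpoints, their order and the analysis populations, but no model. The models therefore come from 2.1 and 3.5. BOP is compared by a chi-square or Fisher test, plus logistic regression "with adjustment to smoking status, GI, medical center and other suspected confounders, if found".

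**The concern.** A factor used to balance the arms belongs in the analysis. Balancing makes the treatment difference less variable. A model without the factor does not see this gain, so it reports a standard error that is too large and a test that rejects too rarely.

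Here the SAP does it both ways. For the primary endpoint, 3.3.1 fits site while 2.1 and 3.5 do not, and nothing says which section governs. The choice between two models for one endpoint is thus still open when results are seen. For the secondary PD endpoints, the only models given lack a site main effect. One of these, PD at week 24 in the 6-8 mm subset, comes first in the fixed testing order, so a narrow miss there stops formal testing of the other three. Section 2.1 could even put a treatment-by-centre interaction into a model that lists no centre main effect.

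Centre differences are plausible: protocol section 6.3.1, as amended, standardises PD and recession measurement between investigators within each centre, no longer between centres.

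**Working it through.** **Step 1: which stratum appears in which model.**

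| Endpoint | SAP section | Site | Smoking | Baseline PD |
|---|---|---|---|---|
| Primary PD, week 24 | 3.3.1 | yes | yes | yes |
| Primary PD, week 24 | 2.1, 3.5 | no | yes | yes |
| Secondary PD (6-8 mm subset at week 24; week 16) | 2.1, 3.5 | no | yes | yes |
| Secondary BOP, logistic | 2.1, 3.5 | yes | yes | not named |
| Exploratory R and RAL | 2.1, 3.5 | no | yes | unclear |

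For a PD outcome I read the listed baseline measurements as including baseline PD.

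**Step 2: inputs.** SAP 1.8 gives 123 per arm, a difference of 0.50 mm, SD 1.30 mm, two-sided 5% and 85% power. The documents do not give r, the share of outcome variance that site explains. I assume 0.02 to 0.10, and show 0 and 0.20 as outer cases.

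**Step 3: the plan's own figure.** SE = 1.30 × √(2/123) = 0.1658, and 0.50/0.1658 = 3.016. Normal-approximation power = Φ(3.016 − 1.960) = Φ(1.056) = 85.5%. The noncentral t gives 85.2% at 123 per arm and 84.9% at 122. The plan's 123 reproduces.

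**Step 4: effect of leaving site out.** With arms balanced within site, the true standard deviation of the difference is 0.1658 × √(1−r). A model without site still reports 0.1658. Hence:

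- SE ratio = 1/√(1−r)
- true alpha = 2 × [1 − Φ(1.960/√(1−r))]
- power, site omitted = Φ(1.056/√(1−r))
- power, site fitted = Φ(3.016/√(1−r) − 1.960)

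At r = 0.10, √(1−r) = 0.9487. The SE ratio is 1.054, power with site omitted is Φ(1.113) = 86.7%, and power with site fitted is Φ(1.219) = 88.9%.

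| r (assumed) | SE too large by | True alpha | Power, omitted | Power, fitted | Points forgone |
|---|---|---|---|---|---|
| 0 | 0% | 0.050 | 85.5% | 85.5% | 0 |
| 0.02 | 1.0% | 0.048 | 85.7% | 86.1% | 0.4 |
| 0.05 | 2.6% | 0.044 | 86.1% | 87.2% | 1.1 |
| 0.10 | 5.4% | 0.039 | 86.7% | 88.9% | 2.1 |
| 0.20 | 11.8% | 0.028 | 88.1% | 92.1% | 4.0 |

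**Step 5: simulation check.** I used 4,000 trials per setting: 246 patients, 9 sites with 4 lists each, blocks of 6, and one value per patient. I assumed 25% smokers and 60% with PD 6-8 mm. At r = 0.10, omitted against fitted gave alpha 0.043 v 0.050 and power 86.4% v 88.4%, with the reported SE 1.05 times the empirical one. The simulated 0.043 differs from the formula's 0.039 by 0.004; the simulation error is √(0.04 × 0.96/4,000) = 0.003.

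**Step 6: what carries over.** In these formulas the SE ratio and alpha depend only on r, so they also describe the secondary PD models for a given r. The power columns use the primary endpoint's inputs; the SAP gives none for week 16 or for the 6-8 mm subset. Nothing here carries over to the BOP logistic model, where omitting a prognostic covariate also changes the odds ratio being estimated.

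**The case against.** The strongest reply is that this is loose drafting that errs on the safe side. Section 3.3.1 is headed as the principal analysis and fits site, so a reader could reasonably take it to govern the primary endpoint. The error is conservative, power stays above 85% throughout the assumed range, and r is itself an assumption. All of this stands, and it limits the point to an inconsistency with a small cost in efficiency. It does not remove the inconsistency: 3.5 expressly claims the primary endpoint, and no other section supplies a model for the secondary PD endpoints.

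A reader might infer more than the documents support:

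- **That the primary analysis has wrong standard errors and loses power.** Section 3.3.1 fits site, so this would follow only if 2.1 or 3.5 were taken to govern.
- **That the PD stratum is missing from the R and RAL models.** The SAP does not define baseline measurements. The term could mean the outcome's own baseline or could include baseline PD. R and RAL are also exploratory and outside the ordered testing.
- **That the BOP model ignores the stratification.** It already has smoking and medical centre; only baseline PD is not named. Lack of a baseline BOP term is a weak complaint, because entry requires bleeding and/or suppuration on probing and baseline BOP may hardly vary.
- **That the PD stratum matters for every secondary endpoint.** In the 6-8 mm subset it is constant.

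The open-ended confounder clause in the BOP model raises data-driven covariate choice, which is a separate question. The calibration argument is also only suggestive, since a constant centre offset largely cancels in a change from baseline.

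**Conclusion.** The point holds in this form. Site is a randomisation stratum; it is fitted in 3.3.1 and omitted as a main effect from the mixed models in 2.1 and 3.5. The primary endpoint therefore has two conflicting covariate lists, and the two secondary PD endpoints have no site term. The BOP logistic model names no baseline PD.

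For the linear models, at an assumed site share of 2-10%, the SE is about 1-5% too large, true alpha is 0.048-0.039 and about 0.4-2 points of power are forgone. Power remains above the planned 85%, and there is no inflation of false positives. This rests on 1.30 mm being the total SD, on good balance within site, and on one value per patient; the power figures illustrate with the primary endpoint's inputs. The BOP effect is not quantified. The stratification is read from the protocol's summary of changes, because the full current protocol text is not among the documents.

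The change is worth making mainly because it settles one model per endpoint in advance; the gain in precision is a modest bonus.

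**What to change.** Amend the SAP before unblinding:

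1. State that the covariate list in 3.3.1 governs the primary endpoint.
2. Use the same list (clinical centre, smoking, baseline PD, age, gender) in the 2.1 and 3.5 models for PD, R and RAL. For R and RAL, add the outcome's own baseline. Spelling out the list removes the undefined baseline term.
3. Add baseline PD to the BOP logistic model.
4. Define site as clinical centre, since the SAP also uses the word for the four aspects around an implant.
5. Give a rule for pooling small centres, based on centre size alone. This matters most for the BOP logistic model, where cells may be sparse.

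The cost is SAP wording only. Centre, smoking and baseline PD are already recorded because randomisation uses them. With nine centres, the centre term takes 9 − 1 = 8 degrees of freedom against 246 planned patients.

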1.2 Design

This study is a multi-center, randomized, single-blind masking, parallel, two-arm clinical study.

The study duration will be 25-28 weeks (6 months) and will comprise a total of 10 visits: Screening and hygienic phase therapy (weeks -3 to -1), Baseline (week 0), week 2, week 4, week 6, week 8, week 10, week 12, week 16 and week 24 (follow up visit).

During the Baseline visit, eligible patients will be randomized to one of the following treatment regimens:

Treatment 1 – Subgingival debridement + Chlorhexidine Gluconate chip (PerioChip®) inserted every fortnight, for the first 12 weeks.

Treatment 2 – Subgingival debridement.

These treatments will be applied for at least 1 (one) and not more than 2 (two) implants in the oral cavity with clinical and radiographical signs of peri-implantitis. Peri-implantitis is defined as marginal bone loss of at least 3 mm from implant shoulder, and at least 2 mm distal and mesial supporting bone left from the apex to the coronal direction, in combination with bleeding and/or suppuration on probing and a peri-implant Probing Depth (PD) of 5-8 mm.

All pocket measurements (PD, BOP and R) and chip insertions will be made in the same order of procedures every time.

The same examiner will perform all the measurements during the study.

The person (physician/hygienist) placing the Chlorhexidine chips in the periodontal pockets or performing the Subgingival debridement, according to the randomization, will not be involved in target pockets measurements (i.e. the examiner and the physician/hygienist placing the chip or performing the Subgingival debridement will be two different persons).

In each patient meeting the entrance criteria, the deepest periodontal pocket of at least 1 (one) and no more than 2 (two) implant/s (if available) will be selected as a target pocket, and will be used for chip/s insertion or Subgingival Debridement and as the primary efficacy end-point.

The target pocket in the selected implant/s, will be treated at each visit with the same treatment arm, initiated at Baseline visit, as described below.

Implant/s which were not selected as target implant/s will be treated as per the investigators discretion as long as it does not affect the study inclusion/exclusion criteria (e.g. treatment with antibiotics or surgery next to a target implant included in the study).

Treatment 1: (PerioChip®)

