3.4 Secondary Efficacy Endpoints

The secondary efficacy endpoints are:

- PD measurement at week 24 compared to baseline in patients with baseline PD measurement of 6-8 mm inclusive.
- Bleeding on Probing (BOP) measurements at week 16 and 24 compared to baseline.
- PD measurement at week 16 compared to baseline.

The analysis of the secondary endpoints will be based on ITT, mITT, PP and PP2 populations.

Multiplicity

The secondary efficacy endpoints will be analysed according to pre-defined order:

1. PD changes at 24 weeks from baseline in patients with baseline PD of 6-8 mm inclusive.
2. BOP changes at 24 weeks from baseline
3. BOP changes at 16 weeks from baseline
4. PD changes at 16 weeks from baseline

The following stages will be applied:

1. The 1st secondary endpoint in the ordered list will be tested at 5% significance level. If it achieves statistical significance then the 2nd secondary endpoint will be analysed (stage 2). Otherwise the other secondary endpoints in the list will not formally be tested.
2. The 2nd secondary endpoint in the ordered list will be tested at 5% significance level. If it achieves statistical significance then the 3rd secondary endpoint will be analysed (stage 3). Otherwise the other secondary endpoints in the list will not formally be tested.
3. The process will continue for all the secondary endpoints according to the list until a secondary endpoint is not significant or until all secondary endpoints have been found significant.

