14.2 Efficacy Data

- 14.2-1 Summary Statistics of Pocket Depth (PD) at baseline and weeks 8, 12, 16, and 24 for target sites
- 14.2-2 **Primary Endpoint Analysis**
- 14.2-2.1 Summary Statistics of Pocket Depth (PD) Change at week 24 for target implants (by-pocket, ITT)
- 14.2-2.2 Summary Statistics of Pocket Depth (PD) Change at week 24 for target implants (by-pocket, mITT)
- 14.2-2.3 Summary Statistics of Pocket Depth (PD) Change at week 24 for target implants (by-pocket, PP)
- 14.2-2.4 Summary Statistics of Pocket Depth (PD) Change at week 24 for target implants (by-pocket, PP2)
- 14.2-2.5 Summary Statistics of Pocket Depth (PD) Change at week 24 for target implants (by-patient, ITT)
- 14.2-2.6 Summary Statistics of Pocket Depth (PD) Change at week 24 for target implants (by-patient, mITT)
- 14.2-2.7 Summary Statistics of Pocket Depth (PD) Change at week 24 for target implants (by-patient, PP)
- 14.2-2.8 Summary Statistics of Pocket Depth (PD) Change at week 24 for target implants (by-patient, PP2)
- 14.2-3 **Secondary Endpoint Analysis**
- 14.2-3.1 Summary Statistics of Pocket Depth (PD) Change at week 24 for target implants, patients with PD 6-8 mm at baseline (by-pocket, ITT)
- 14.2-3.2 Summary Statistics of Pocket Depth (PD) Change at week 24 for target implants, patients with PD 6-8 mm at baseline (by-pocket, mITT)
- 14.2-3.3 Summary Statistics of Pocket Depth (PD) Change at week 24 for target implants, patients with PD 6-8 mm at baseline (by-pocket, PP)
- 14.2-3.4 Summary Statistics of Pocket Depth (PD) Change at week 24 for target implants, patients with PD 6-8 mm at baseline (by-pocket, PP2)
- 14.2-3.5 Summary Bleeding on Probing (BOP) Change at week 16 and 24 for target implants (by-pocket, ITT)
- 14.2-3.6 Summary Bleeding on Probing (BOP) Change at week 16 and 24 for target implants (by-pocket, mITT)
- 14.2-3.7 Summary Bleeding on Probing (BOP) Change at week 16 and 24 for target implants (by-pocket, PP)
- 14.2-3.8 Summary Bleeding on Probing (BOP) Change at week 16 and 24 for target implants (by-pocket, PP2)

Table number	Table Title
14.2-3.9	Summary Statistics of Pocket Depth (PD) Change at week 16 for target implants (by-pocket, ITT)
14.2-3.10	Summary Statistics of Pocket Depth (PD) Change at week 16 for target implants (by-pocket, mITT)
14.2-3.11	Summary Statistics of Pocket Depth (PD) Change at week 16 for target implants (by-pocket, PP)

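### Bleeding on probing, steps 2 and 3 of the secondary sequence, is tested with no allowance for patients who contribute two target pockets

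*SAP*

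**What the plan says.** - **Unit.** SAP 1.2 randomises the patient and selects as target pockets "the deepest periodontal pocket of at least 1 (one) and no more than 2 (two) implant/s". Both pockets stay in the arm assigned at baseline.
- **Tests for BOP.** SAP 3.5, whose methods are stated to serve the primary and secondary endpoints, says "analysis for BOP for the target implant/s measured at each visit will be analyzed by a Chi-square test", with Fisher's exact test as the alternative. The same sentence covers the counts of pockets with at least 1 mm and at least 2 mm PD reduction. It continues: "Logistic regression will be applied for testing the above differences with adjustment to smoking status, GI, medical center and other suspected confounders, if found". Section 2.1 has the same wording.
- **Where clustering is handled.** For PD, section 3.3.1 states: "Patient and pocket will be entered as random effects". Sections 2.1 and 3.5 limit that mixed model to PD, recession and attachment level.
- **Unit of analysis.** Section 3.5 adds: "All treated pockets will be taken into account to create a by-pocket analysis in addition to the by-patient analysis". No rule turns two pockets into one patient-level BOP result. In Appendix I the four secondary BOP tables (14.2-3.5 to 14.2-3.8) are all by-pocket. By-patient efficacy tables are listed only for the primary endpoint (14.2-2.5 to 14.2-2.8).
- **Role of BOP.** In the Multiplicity part of section 3.4, BOP at week 24 is second and BOP at week 16 third in the fixed order. For step 2: "The 2nd secondary endpoint in the ordered list will be tested at 5% significance level". Step 3 follows the same rule.

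**The concern.** Chi-square, Fisher and ordinary logistic regression all treat each observation as independent. Two pockets in one mouth share the patient's hygiene, smoking, host response and allocation, so a positive correlation is to be expected. Counting them as two independent units overstates the information: standard errors are too small, confidence intervals too narrow and p-values too low.

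The SAP allows for this in the PD model but not for BOP. It also does not say which of chi-square, Fisher or logistic regression decides steps 2 and 3.

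The exposed situation is a trial in which step 1 (PD in the 6-8 mm group) succeeds and BOP has no true treatment effect. The sequence then relies on a valid 5% test at step 2, and a false BOP claim could arise from counting some patients twice. Where no endpoint has an effect, gatekeeping holds a formal BOP claim at or below about 5%, provided the mixed model decides step 1.

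**Working it through.** **The plan's own figure.** SAP 1.8 uses a difference of 0.50 mm, SD 1.30, two-sided 5% and 85% power. The t-test calculation gives 122.4, so 123 per arm, with power 85.2% at 123. This reproduces. It concerns PD only; the SAP states no power for BOP.

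**Inputs not in the documents.** The share *f* of patients with two target implants and the within-patient correlation of BOP (ICC) are assumptions, shown over a range.

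**Design effect.** With cluster sizes 1 and 2, the mean size is 1 + f and the mean squared size is (1 − f) + 4f = 1 + 3f. Hence

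DEFF = 1 + ICC × [(1 + 3f)/(1 + f) − 1] = 1 + ICC × 2f/(1 + f).

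True level of the nominal 5% test = 2 × [1 − Φ(1.96/√DEFF)]. The correct interval is wider by √DEFF − 1.

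Example, f = 0.5 and ICC = 0.5: DEFF = 1 + 0.5 × 1/1.5 = 1.33; 1.96/√1.33 = 1.70; level = 9.0%; widening 15%. About 184 pockets per arm (123 × 1.5) then carry the information of about 138.

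| f | ICC | DEFF | True level | CI widening |
|---|---|---|---|---|
| 0.1 | 0.1 | 1.02 | 5.2% | 1% |
| 0.2 | 0.3 | 1.10 | 6.2% | 5% |
| 0.5 | 0.3 | 1.20 | 7.4% | 10% |
| 0.5 | 0.5 | 1.33 | 9.0% | 15% |
| 0.7 | 0.5 | 1.41 | 9.9% | 19% |

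**Does covariate adjustment help?** Simulation under no BOP effect used 246 patients 1:1, nine centres, 50% BOP, beta-binomial pockets, and smoking, GI and centre explaining part of the between-patient variation. The BOP rate and covariate strengths are assumed. There were 10,000 runs per setting, with Monte Carlo error of about 0.2 to 0.3 points. Rejection rates at nominal 5%:

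| f, ICC | Chi-square | Adjusted logistic, no clustering | Same model, patient-clustered variance |
|---|---|---|---|
| 0.1, 0.1 | 5.6% | 6.0% | 5.2% |
| 0.2, 0.3 | 6.3% | 6.3% | 4.9% |
| 0.5, 0.3 | 7.7% | 8.1% | 5.5% |
| 0.5, 0.5 | 8.6% | 8.9% | 4.9% |
| 0.7, 0.5 | 9.5% | 9.3% | 4.5% |

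A separate simulation without covariates (20,000 runs per setting, BOP rates 50% and 70%) gave 8.7% to 9.0% for the pocket-level test at f 0.5, ICC 0.5. The patient-clustered test rejected in about 5% of runs in every setting. With ICC = 0 there was no inflation beyond simulation error.

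**Chance of a false formal week 24 claim.** This is P(step 1 passes) × level, taking the two as independent. With an assumed 85% for step 1, borrowed from the primary power: 0.85 × 5.2% = 4.4% (0.1, 0.1); 0.85 × 6.2% = 5.2% (0.2, 0.3); 0.85 × 9.0% = 7.6% (0.5, 0.5).

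**The case against.** The strongest reply is that the SAP mentions a by-patient analysis, and presents the by-pocket one as the addition, just before the BOP sentence in section 3.5. A by-patient chi-square would have no clustering problem. Nor do the table labels settle the matter alone: the secondary PD tables are also by-pocket only, although the PD model has a patient effect. It is fair that the pocket-level reading is partly inferred. But no patient-level BOP outcome is defined, section 3.4 does not repeat the by-patient provision that section 3.3 makes for the primary endpoint, and the logistic model has no patient term. A programmer following the text has only a pocket-level BOP test to run.

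The second reply concerns size. A second implant is taken only if available, so f may be small and the excess trivial. Step 1 also uses only the 6-8 mm patients, so 85% may be too high. Keeping 0.50 mm and SD 1.30, with 40%, 60% or 80% of patients qualifying, step 1 power is about 48%, 65% or 77% (normal approximation). The false-claim figure becomes 3.0%, 4.0% or 4.8% at (0.2, 0.3), and 4.3%, 5.8% or 6.9% at (0.5, 0.5). This stands for the unconditional figure. It does not repair the level at the BOP steps, which should be 5% even when step 1 is certain to pass. A larger effect in deep pockets would raise step 1 power again.

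Third, the pocket counts lie outside the formal sequence, so the error-rate consequence falls on BOP. That is correct.

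Fourth, a defined patient-level BOP outcome tested by chi-square or Fisher would also be valid, and an independence GEE gives two-implant patients more weight. Both are true; neither defends the text as it stands.

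**Conclusion.** The concern holds. As written, BOP at weeks 24 and 16 is assigned tests that ignore within-patient clustering, and the SAP does not name the one that decides. Over the assumed range the true level is 5.2% to 9.9% instead of 5%, and correct intervals are 1% to 19% wider. The size depends on f and ICC, which the documents do not give; with few two-implant patients or little correlation it is negligible.

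The consequence is confined to two secondary steps and to the pocket-count analyses outside the sequence. The principal PD mixed model, which has a patient random effect, and the 123 per arm are not affected. For PD, only by-pocket versions of the simpler supporting tests share the problem. This should be fixed; it does not threaten the primary conclusion.

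**What to change.** In sections 2.1, 3.4 and 3.5, state that BOP at week 24, and then at week 16, is decided by a logistic GEE clustered on patient:

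- independence working correlation and robust variance;
- two-sided 5%;
- covariates already named in the SAP: smoking status, GI and medical centre;
- treatment odds ratio reported with its 95% confidence interval.

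Use the same model for the counts of pockets with at least 1 mm and at least 2 mm PD reduction. Label as descriptive the pocket-level chi-square and Fisher tests and any by-pocket PD t-test, rank or median test, ANOVA or median-split logistic regression.

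The cost is SAP wording and a few lines of code, with no new data. BOP intervals widen by about 5% to 15% for f 0.2 to 0.5 and ICC 0.3 to 0.5. If clustering proves negligible, almost nothing is lost.
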